## II. Objectives

### A. Primary objectives:

1. Studies in tissue: The primary objective of this study will be to determine associations between PD-L1 expression (quantitatively determined as a continuous variable) in tumor tissue at baseline and an objective response to protocol treatment.
2. Peripheral blood studies: To determine association between changes in percentages of circulating activated T-cells, specifically CD8+/HLA-DR+/Ki-67+ T cells and an objective response to protocol treatment.

B. Exploratory studies

1. To associate levels of tumor infiltrating CD8+ T-cells, and PD-L1 expression defined categorically, and also in specific cell populations such as tumor cells and tumor infiltrating lymphocytes with response
2. As tissue allows, to explore correlations between response and multiple immunologic biomarkers including PD-1, CTLA-4, MHC-1, MHC-2, Lag-3, B2M, Na channel and other exploratory multiplex IF to determine expression levels of these biomarkers in components of the tumor microenvironment and in relation to each other
3. To evaluate mechanisms of resistance by comparing immunologic markers in sequential biopsies and biopsies taken at progression if available
4. To explore correlations between PD-L1 expression and CD8 + T-cell tumor infiltration with overall tumor mutational burden as determined by whole-exome and targeted sequencing to be performed through the parent NCI MATCH study
5. To explore associations between changes in a panel of circulating immune populations and immunologic cytokines with response Methodology

III. **Methodology**

Summary:

Correlative science will involve immune evaluation of archival tissue, serum and PBMCs obtained from multiple time points. PD-L1 expression and CD8+ T-cell infiltration will be evaluated on cut FFPE slides as below to correlate with response. We will also examine changes in these biomarkers over time when sequential biopsy specimens are available. Additional tissue, when available will be used for multiplexed IF and assayed for other immunologic markers as described in detail below. CyTOF will primarily examine changes in circulating activated T-cells over the course of therapy as a predictor of response but will also explore other immune subsets and cytokines.

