## IV. Statistical Considerstions

### A. Endpoints

1. Primary
  - a) PD-L1 positivity
  - b) Percent of circulating, activated CD8+/HLA-DR+/Ki-67+ T-cells
2. Secondary
  - a) PD-L1 positive cases

- b) Infiltration of lymphocytes per high powered field
- c) Exploratory analyses of expression levels of various serum cytokine and tumor immune biomarkers

B. Case selection and Sample Size

All consenting cases with adequate biospecimen available from the Z1D subarm.

Sample size estimate: 44 patients for tissue analyses, 37 patients for blood analyses

C. Analysis plan:

Regarding the primary endpoint of PD-L1 expression in tumor tissue, an unpaired t test will be used to compare the percent positive tumor cells in responders vs. non-responders. Responders will be determined using the primary endpoint of the trial – objective tumor response. Using the data provided in the supplementary appendix to Le et al. as a basis for the power calculations (Le DT, Uram JN, Wang H, et al. PD-1 blockade in tumors with mismatch-repair deficiency. N Engl J Med 2015;372:2509-20) it is assumed that PD-L1 expression, measured as a percentage of positive cells, will have a mean percentage of roughly 20% and a standard deviation of about 10%. Using these figures and assuming also that roughly 24% of all patients in this subarm will be responders, with approximately 44 patients with tissue available (roughly 11 responders and 33 non-responders) there is at least 80% power to detect a mean difference of 10% (e.g., 29% versus 19%) in PD-L1 expression between responders and non-responders using a two-sided 0.05 level t-test. The 24% figure used for the calculations was chosen based on the results of this arm recently presented at SITC.

Given the small sample size of this subarm, a categorical analysis to correlate objective response with PD-L1 positivity (for example via Fisher's exact test using a 5% cutpoint for PD-L1 positivity) will not have meaningful power, hence the proposed analyses will be done on the continuous PD-L1 metric and any categorical analyses will be considered exploratory. Following the logic of the power analyses above, there is 80% power to detect a 1.00 standard deviation difference in the means of any quantitative biomarker between responders and non-responders (assuming the overall response rate above) using a two-sided 0.05 level t-test.

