The primary objective is to examine the association between a single biomarker (PD-L1 expression) and response. Thus, no statistical adjustments are planned for this analysis. Other planned IF and IHC testing is exploratory and largely based on mechanistic hypotheses (e.g. exploring for treatment resistance as a consequence of defects in the MHC I or MHC II expression and antigen presentation pathways). Therefore, exploratory analyses will be descriptive in nature with no planned adjustment for multiple testing.

When genomics data are available from the NCI MATCH study we may perform exploratory analyses to examine associations with protein expression across the markers tested. Specifically, there are immediate plans to attempt to look at numbers of MOIs based on the NCI MATCH assay as a proxy for high mutational burden for arm Z1D and correlate this with response. We will correlate this measure with our primary endpoint of PD-L1 expression as well as with our other exploratory endpoints.

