The primary endpoint of studies to be conducted on peripheral blood will evaluate changes in percentage of circulating CD8+/HLA-DR+/Ki-67+ T cells and response. We will compare the change in percentage of this cell population between responder and non-responder patients. To give a sense of power for studies to be done on paired tissue and blood samples (baseline versus progression), and blood samples (paired within patient comparing baseline vs progression) for analyses of various quantitative biomarkers being proposed here, differences will be taken for all measures and the hypotheses is that biomarkers will change (increase or decrease) post therapy. PD-L1 expression on tumor cells, infiltrating and circulating T-cell populations, myeloid derived suppressor cells, and immunologic cytokines and other immunologic markers. Assuming that within this cohort we will obtain paired samples on conservatively 40 patients, using a two-sided 0.05 level paired t-test there is at least 80% power to detect a 0.46 SD change in mean of a quantitative correlative parameter using a two-sided test with 5% type I error. Quantitative measure will be transformed to attain normality or appropriate non-parametric tests will be conducted. With this level of consent for these studies in this cohort there is sufficient power for meaningful analyses. Power for these tests will be further improved if a greater percentage of the cohort of 47 patients consent and provide post-baseline (progression) samples for analysis.

D. Rationale for the sample size estimate:

As described above, assuming that roughly 24% of all patients in this subarm will be responders, with 44 patients (expected distribution to be roughly 11 responders and 33 non-responders) there is at least 80% power to detect a mean difference of 10% (e.g., 29% versus 19%) in PD-L1 expression between responders and non-responders using a two-sided 0.05 level t-test.

For the blood studies, assuming approximately 40 patients have usable specimens pre and post treatment, using a two-sided 0.05 level paired t-test there is at least 80% power to detect a 0.46 SD change in mean of a quantitative correlative parameter using a two-sided test with 5% type I error.

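### Does the single-biomarker reason for not adjusting contradict the second primary biomarker, measured in blood?

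*Protocol*

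**What the plan says.** All the relevant text is in Appendix V of the Protocol.

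- Section II.A gives two primary objectives, one per specimen type. The first opens "Studies in tissue: The primary objective of this study will be to determine associations between PD-L1 expression". The second opens "Peripheral blood studies: To determine association between changes in percentages of circulating activated T-cells". Both relate the marker to objective response.
- Section IV.A lists two primary endpoints: PD-L1 positivity and "Percent of circulating, activated CD8+/HLA-DR+/Ki-67+ T-cells".
- Section IV.C first sets out the PD-L1 comparison of responders with non-responders and its power. It then says that the primary objective is to "examine the association between a single biomarker (PD-L1 expression) and response. Thus, no statistical adjustments are planned for this analysis". It goes on to call the other immunofluorescence and immunohistochemistry work exploratory, and concludes that "exploratory analyses will be descriptive in nature with no planned adjustment for multiple testing".
- A short paragraph on genomic data follows. It plans to use the count of mutations of interest as a proxy for mutational burden, and ends: "We will correlate this measure with our primary endpoint of PD-L1 expression as well as with our other exploratory endpoints".
- The blood part of IV.C then begins: "The primary endpoint of studies to be conducted on peripheral blood will evaluate changes in percentage of circulating CD8+/HLA-DR+/Ki-67+ T cells and response". It adds: "We will compare the change in percentage of this cell population between responder and non-responder patients".

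**The concern.** Taken alone, the sentence in IV.C speaks of the primary objective in the singular, without limiting it to tissue, and makes the single biomarker the only reason for not adjusting. The same appendix declares a second primary biomarker, tested against the same outcome in overlapping patients of one subarm. If the reason covered the whole appendix, it would be untrue.

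The closing sentence of the genomics paragraph seems to confirm this. It names PD-L1 as the primary endpoint and calls the others exploratory, which appears to leave no room for a blood primary.

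Two things would be at stake. Two primary tests at 5% each carry a joint false-positive risk above 5%. And if IV.C could be cited for one primary with everything else descriptive, while II.A and IV.A could be cited for two, the label of the T-cell result could be chosen after the data were seen.

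**Working it through.** **The plan's own figure.** Inputs from IV.C: difference 10 percentage points, SD 10, 11 responders and 33 non-responders, two-sided 0.05.

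- Standardised difference: 10/10 = 1.0.
- Noncentrality: 1.0 × √(11 × 33/44) = √8.25 = 2.87.
- Power: 80.1% by the noncentral t distribution and 81.9% by the normal approximation. The stated figure of at least 80% reproduces.

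**Joint error if both primaries were tested at two-sided 0.05.** IV.C attaches no level directly to the blood comparison. The 0.05 is taken from its general statement on quantitative biomarkers compared between responders and non-responders.

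| Situation | Chance of at least one false association |
|---|---|
| Both nulls true, independent tests | 1 − 0.95² = 9.75% |
| Both nulls true, correlation 0.3 / 0.5 / 0.9 | 9.5% / 9.1% / 7.0% |
| Both nulls true, upper bound | 0.05 + 0.05 = 10% |
| Exactly one null true | 5% |
| Neither null true | 0% |

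Each test's own error is 5% in every row where its null is true. The figures above 5% matter only if the two tests are one family with a single 5% claim. Appendix V makes no such claim.

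**What the sentence refers to.** Four features fix its scope.

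1. *Position.* It follows the PD-L1 test and its power calculation, and precedes the blood paragraph. Section II.A uses the same order: tissue, then blood.
2. *Its own limit.* The decision not to adjust is made for the analysis in hand, which is the PD-L1 comparison just described.
3. *The contrast drawn.* PD-L1 is set against other immunofluorescence and immunohistochemistry assays. Both are tissue methods. Blood is not mentioned in that paragraph.
4. *Match with II.A.* Item 1 there also speaks of the primary objective in the singular, under a tissue label: "Studies in tissue: The primary objective of this study will be to determine associations between PD-L1 expression". The IV.C sentence restates that item.

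Read this way the premise is true: the tissue study has one primary biomarker.

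**The genomics sentence.** It says what the mutation count will be correlated with. It is not a list of all endpoints. It corresponds to exploratory objective 4 in Section II.B, which relates mutational burden to PD-L1 expression and CD8+ T-cell infiltration of the tumour, both tissue measures. Section II states no analysis of the blood marker against genomic data, so omitting the blood primary here contradicts nothing.

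**Could the T-cell marker be relabelled as descriptive?** It is called primary in II.A, in IV.A and in the blood part of IV.C, and exploratory nowhere. The sentence making exploratory analyses descriptive is drawn as a consequence of the remark on other immunofluorescence and immunohistochemistry testing. Section III measures the T-cell marker by CyTOF, which is neither.

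**The case for a change.** The strongest case for a defect is that II.A marks its tissue objective as tissue and IV.C marks its blood endpoint as blood, while the sentence between them drops the qualifier. It gives the only reason for not adjusting, and no sentence in the appendix says whether the two primaries are one family or separate hypotheses. A reader who meets the paragraph in isolation could conclude that there is one primary and that all else is exploratory.

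Part of this stands. The qualifier is absent, and adding it would help a hurried reader. It is also true that the level for the blood comparison must be read from the general statement in IV.C.

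The rest does not stand. A missing qualifier is an error only if the surrounding text leaves the scope open, and here the position, the limiting words, the contrast and the match with II.A close it. Whether tissue and blood should share one error rate is a separate design choice, and a formal rule for it could be left to a statistical analysis plan. Treating them as one family would also have a cost: at 0.025 each, PD-L1 power falls from 80.1% to 70.7%, and the difference detectable with 80% power rises from 1.00 to 1.11 SD. Nothing in Appendix V commits the investigators to that.

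**Conclusion.** The concern does not hold. The single-biomarker sentence is correct for the tissue study it describes and does not conflict with the two primary objectives in II.A, the two primary endpoints in IV.A or the blood part of IV.C. The 9.75% is sound arithmetic for two independent tests with both nulls true, but it measures a joint claim the plan never makes. Each primary association keeps its own 5% error, PD-L1 power stays at 80.1%, and no test, sample size or efficacy conclusion changes.

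This rests on reading the sentence within its paragraph and on tissue and blood being separate questions, as II.A sets them out. It would need to be reopened if the two results were later combined into one claim at an overall 5% level. It says nothing about whether the blood comparison is adequately powered, which is a different question.

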We propose to evaluate associations with PD-L1 expression measured as a continuous metric of positivity (as described above) as opposed to a single cutoff. Exploratory analyses will assess specific cutpoints of PD-L1 positivity (e.g. 1%, 5%, 10%, etc.) as potential biomarkers, as these cutpoints have been described previously in the literature. To our knowledge there are unfortunately no on-treatment pathologic specimens available and therefore magnitude of change on treatment cannot be assessed. As mentioned in the above statistical analysis plan, assuming that within this cohort we will obtain paired samples on conservatively 40 patients that yield evaluable data for our flow-cytometric biomarkers, using a two-sided 0.05 level paired t-test there is at least 80% power to detect a 0.46 SD change in mean of a quantitative correlative parameter using a two-sided test with 5% type I error. Quantitative measures will be transformed to attain normality or appropriate non-parametric tests will be conducted as appropriate. We will also compare changes between responder and non-responder groups for the purpose of our analyses.

E. Statistical considerations for secondary objectives (if applicable)

Our secondary objectives for testing multiple biomarkers in tissue and serum are exploratory. However, these objectives are based on strong biologic rationale

and may also identify future targets for combinations with PD-1 inhibitors in patients with mismatch repair deficiency or other tumors.

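### Appendix V's blood power does not hold at its own blood sample size of 37, and the blood sample-size rationale is for a paired test, not for the primary responder comparison, whose two draws are also not named

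*Protocol*

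**What the plan says.** All references are to the protocol. Appendix V (CS-MATCH-0005) has a primary blood objective (II.A, item 2): the association between change in the percentage of circulating CD8+/HLA-DR+/Ki-67+ T cells and objective response. IV.C turns this into a group comparison: "We will compare the change in percentage of this cell population between responder and non-responder patients".

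**Sample size.** IV.B gives 44 patients for tissue and "37 patients for blood analyses". IV.D bases the blood sample size on a different count, "assuming approximately 40 patients have usable specimens pre and post treatment", and later repeats it: "assuming that within this cohort we will obtain paired samples on conservatively 40 patients that yield evaluable data for our flow-cytometric biomarkers".

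**Power.** For blood, IV.C and IV.D say that with a two-sided 0.05 paired t-test "there is at least 80% power to detect a 0.46 SD change in mean of a quantitative correlative parameter". Separately, IV.C gives a between-group figure of 80% power at 1.00 SD for any quantitative biomarker. It follows the tissue calculation (44 patients, 24% responders, 11 vs 33).

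**Timing.** Neither the objective nor the comparison names two visits. In a passage meant to give a sense of power, IV.C refers to "blood samples (paired within patient comparing baseline vs progression) for analyses of various quantitative biomarkers being proposed here", and to patients who "consent and provide post-baseline (progression) samples for analysis". Section 4.1 (footnote J) and section 6.1.1 schedule research blood before treatment, after Cycle 2 (before Cycle 3) and at the end of treatment.

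**The concern.** A reader of IV.D would take 40 patients and 0.46 SD as the sensitivity of the blood study. Neither figure matches the primary blood analysis. The planned number is 37, so a count described as conservative is above the plan's own estimate. The paired test asks whether a marker moves on average over time. The primary question is whether it moves differently in responders and non-responders, with only about 9 or 10 responders. The generic 1.00 SD statement is for the right kind of comparison but rests on seven more patients than IV.B gives for blood.

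The visit gap matters less but is real. The Appendix V introduction wants an early marker of benefit, and its methodology summary wants change as a predictor of response. A sample taken at progression suits that aim badly: it comes after the response it should predict, and responders still on treatment would not yet have one. IV.D says of tissue that "there are unfortunately no on-treatment pathologic specimens available and therefore magnitude of change on treatment cannot be assessed". That reason does not apply to blood, which has a scheduled post-Cycle 2 draw that section IV never mentions. With the pair open, the one primary blood test could be run on different pairs that answer different questions.

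**Working it through.** **Inputs**
- Blood patients: 37 (IV.B); 40 (IV.C, IV.D).
- Tissue: 44 patients, 11 responders vs 33 non-responders (IV.C).
- Response rate 24% (IV.C): 0.24 × 37 = 8.9, taken as 9 vs 28; 0.24 × 40 = 9.6, taken as 10 vs 30.
- Two-sided alpha 0.05. Effects are in SD units; for blood, the SD of the within-patient change.

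**Formulas** (noncentral t)
- Paired: noncentrality = d × √n, df = n − 1.
- Two groups: noncentrality = d / √(1/n₁ + 1/n₂), df = n₁ + n₂ − 2.
- Power = probability that |t| exceeds its 0.975 critical value.

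**Step 1. Reproduce the plan's figures.**
- Paired, n = 40, d = 0.46: 0.46 × √40 = 2.909, df 39, critical value 2.023; power 81.0%. The stated figure holds.
- Tissue, 11 vs 33, d = 1.00: √(1/11 + 1/33) = 0.348, so 1/0.348 = 2.872, df 42, critical value 2.018; power 80.1%. The stated figure holds.

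**Step 2. The paired test at IV.B's 37.**
0.46 × √37 = 2.798, df 36, critical value 2.028; power 77.7%. For 80%, 0.473 SD is needed.

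**Step 3. The responder comparison at the blood numbers.**
- 9 vs 28, d = 1.00: √(1/9 + 1/28) = 0.383, noncentrality 2.610, df 35, critical value 2.030; power 71.8%.
- 10 vs 30, d = 1.00: √(1/10 + 1/30) = 0.365, noncentrality 2.739, df 38, critical value 2.024; power 76.1%.

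| Split | Power at 1.00 SD | SD for 80% power |
|---|---|---|
| 11 vs 33 (tissue, 44) | 80.1% | 0.998 |
| 10 vs 30 (40) | 76.1% | 1.050 |
| 9 vs 28 (37) | 71.8% | 1.104 |

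One responder more or fewer among 37 does not change the picture: 8 vs 29 gives 68.3% (80% at 1.15 SD) and 10 vs 27 gives 74.7% (80% at 1.07 SD).

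**Step 4. The 0.46 SD figure applied to the responder comparison.**
Power for a 0.46 SD difference between groups is 21.5% at 9 vs 28 and 23.3% at 10 vs 30. So 0.46 SD cannot serve as the rationale for the primary blood comparison.

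**Step 5. Visits.**
Section IV names one blood pair, baseline with progression, inside a power illustration. IV.D speaks more loosely of specimens before and after treatment. Sections 4.1 and 6.1.1 schedule three draws, and progression as such is not one of them. It often coincides with discontinuation, because section 3.1 treats until progression, but not always, because section 3.7 allows treatment beyond it. No section ties the primary change to two of the three draws.

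**The case against.** **On power.** The 0.46 SD figure is called a paired t-test each time it appears, and IV.C does give a between-group figure. A reader might infer that the plan has no power statement for a responder comparison, or that it overstates sensitivity by the ratio of 1.10 to 0.46. The documents do not support that: the fair benchmark is the plan's own 1.00 SD, and the shortfall is 1.00 against 1.10 SD at 37 patients. The paired figure loses only about three points at 37. All consenting cases with adequate specimens are used, so no recruitment decision turns on the difference. These points limit the size of the problem. They do not remove it: 80% is claimed where about 72% is available, and IV.D offers only the paired figure as the blood rationale.

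**On timing.** A reader might infer that the plan defines the primary change as baseline to progression, or that section IV contains several colliding definitions. It does not go that far. The progression wording sits in a power illustration, and the phrases in section IV can all be read as one first-to-last pair. Harm from a progression sample is conditional on that pair being used, and the number of responders it would lose cannot be derived from the document. The objective itself asks only for an association; prediction comes from the introduction and methodology summary. What stands is that the pair is not named and the on-treatment draw is not mentioned.

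**On leaving this to a later plan.** Visit definitions often are left there, but IV.D refers to this text as the statistical analysis plan, and the patient counts and power are stated here.

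**Conclusion.** The power statements for blood are wrong as written. At IV.B's 37 patients the paired test has 78% power at 0.46 SD, not at least 80%. The responder comparison has about 72% at 1.00 SD, not 80%, and needs about 1.10 SD for 80%. At 40 patients the paired claim holds (81%), but the responder comparison still reaches only 76% at 1.00 SD and needs about 1.05 SD. These results rest on the plan's 24% response rate, on rounding to whole patients, and on a two-sample t-test with equal variances and roughly normal change scores.

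The missing visit pair is a secondary gap in definition, not a formal contradiction. It is worth closing because the only blood pair named suits the predictive aim poorly.

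This should be fixed, but its reach is limited to the correlative blood objective. The arm's response endpoint is untouched.

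**What to change.** In Appendix V, section IV:

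1. Reconcile 37 (IV.B) with 40 (IV.C, IV.D).
2. State blood power for the two-group comparison at the reconciled number: 9 vs 28, about 72% at 1.00 SD and 80% at about 1.10 SD; or 10 vs 30, about 76% and 80% at about 1.05 SD.
3. Limit the 1.00 SD statement to the 44-patient tissue analysis.
4. Say that 0.46 SD is not the power of the primary responder comparison.
5. Name the visit pair for the primary blood change before analysis. Pre-treatment to post-Cycle 2 fits the predictor and early-marker aim. Keep pairs of baseline with discontinuation or progression exploratory, and align the wording with sections 4.1 and 6.1.1.

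**Cost.** These are wording changes; the sample is already scheduled. The suggested pair has two downsides. Patients who stop before Cycle 3 leave the comparison, which is itself a selection related to outcome, so report them separately and use their discontinuation sample in a sensitivity analysis only. As an assumed range, since the document gives none, losing 4 to 8 non-responders from 9 vs 28 (leaving 9 vs 24 to 9 vs 20) lowers power at 1.00 SD to between 70% and 67%. Also, the draw falls near the first disease assessment (every 2 cycles), so it is early but does not clearly precede the first response reading.

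### Appendix V applies its 40-pair, at-least-80% power statement to paired tissue, but nothing in the protocol supports 40 baseline-progression tissue pairs

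*Protocol*

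**What the plan says.** Appendix V, IV.C describes a within-patient analysis of change and opens the power discussion with "To give a sense of power for studies to be done on paired tissue and blood samples (baseline versus progression". The measures it lists include two tissue markers, PD-L1 on tumour cells and infiltrating T cells, beside circulating cells and cytokines. The number of pairs is set by "Assuming that within this cohort we will obtain paired samples on conservatively 40 patients", and the conclusion is that "using a two-sided 0.05 level paired t-test there is at least 80% power to detect a 0.46 SD change in mean".

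Other parts of the protocol bear on how many tissue pairs there could be:

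- **Appendix V, II.B (exploratory studies):** the resistance objective rests on "comparing immunologic markers in sequential biopsies and biopsies taken at progression if available".
- **Section 4.1, footnote E:** blood is the routine on-treatment sample, at the end of Cycle 2. Later biopsies are repeat screening where applicable, or a possible research biopsy after consent and registration to Step 8.
- **Appendix V, IV.B:** the expected numbers are "44 patients for tissue analyses, 37 patients for blood analyses".
- **Appendix V, IV.D:** the 40 pairs appear twice more, once for the blood studies and once for the flow-cytometric markers. The same section says of tissue that "there are unfortunately no on-treatment pathologic specimens available and therefore magnitude of change on treatment cannot be assessed".

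**The concern.** One number of pairs, and therefore one power figure, is applied to two sample types whose collection differs. Post-treatment blood is a scheduled sample from consenting patients. Post-baseline tissue depends on a further biopsy that the protocol treats as conditional. A power statement is only as good as its sample size, and the protocol nowhere gives an expected number of tissue pairs.

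Comparing sequential and progression biopsies is how the plan intends to study resistance. If only a few pairs exist, an unchanged marker says little. Read against a stated 80% power, the same result could be taken as evidence that the marker does not change.

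**Working it through.** **Inputs.** Two-sided alpha 0.05, paired t-test, change of 0.46 SD of the within-patient difference and 40 pairs (Appendix V, IV.C). 44 patients with tissue and 37 with blood (IV.B). About 11 responders and 33 non-responders among the 44 (IV.C).

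**Formula.** For n pairs and standardised change d, the test statistic follows a noncentral t distribution with n − 1 degrees of freedom and noncentrality d√n. Power is the probability that its absolute value exceeds the 97.5% point of the central t.

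**Step 1: reproduce the plan's figure.** n = 40, d = 0.46: noncentrality 0.46 × √40 = 2.909, critical value 2.023 on 39 df, power 81.0%. The stated figure is correct for 40 pairs.

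**Step 2: is there any margin?** n = 39: noncentrality 0.46 × √39 = 2.873, power 79.9%. Forty is the smallest number of pairs that reaches 80%.

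**Step 3: what 40 tissue pairs would require.** 40 / 44 = 91% of patients with tissue would need a usable second biopsy. Even if all 33 non-responders progressed and were biopsied, 40 − 33 = 7 of the 11 responders would also have to supply a later biopsy. That is possible, but the protocol gives no basis for expecting it.

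**Step 4: power with fewer tissue pairs.** The protocol gives no count, so every row below 40 is an assumption.

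| Tissue pairs | Power at 0.46 SD | Change detectable with 80% power |
|---|---|---|
| 40 (plan) | 81.0% | 0.45 SD |
| 30 | 68.3% | 0.53 SD |
| 20 | 49.7% | 0.66 SD |
| 10 | 25.6% | 1.00 SD |
| 5 | 12.6% | 1.68 SD |

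**Step 5: the blood figure that would remain.** IV.B expects 37 patients for blood, three fewer than the 40 pairs assumed. n = 37: noncentrality 0.46 × √37 = 2.798, power 77.7%. The change detectable with 80% power is 0.47 SD.

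**The case against.** The strongest defence is that the absence stated in IV.D concerns on-treatment tissue, while the power statement concerns baseline versus progression. These are different time points. A reader might infer from IV.D that no paired tissue exists and that the stated power is impossible. The documents do not support this, because II.B leaves progression biopsies open and Section 4.1 allows a Step 8 research biopsy. This part of the defence stands: 40 tissue pairs are unsubstantiated, not ruled out. Nor does the responder count in Step 3 make 40 impossible, since responders may progress later and Step 8 sampling follows the end of all study treatment.

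Second, the sentence is offered only as an illustration, and both uses in IV.D tie the 40 pairs to blood. That points to loose wording, but it also confirms that the number was not derived for tissue. The sentence names tissue and tissue markers, so it should be corrected.

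Third, sequential and progression tissue work is exploratory. IV.C says exploratory analyses will be descriptive, and the methods section defers hypothesis-generating results to validation in later studies. This limits the harm. It does not remove the inconsistency of attaching a hypothesis, a test and a power figure to the same markers.

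**Conclusion.** The concern holds in a limited form. The at-least-80% power claimed for paired tissue changes has no support in the protocol. It needs at least 40 pairs, or 91% of the patients expected to have tissue, from biopsies that the protocol treats as conditional. If the true number were between 10 and 30, power at 0.46 SD would be about 26% to 68%; that range is assumed, because no count is given.

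The finding does not establish that tissue pairs are absent, and the plan's arithmetic is not in error. The primary tissue analysis compares baseline PD-L1 between responders and non-responders, uses no paired tissue, and is unaffected.

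Limiting the statement to blood is not enough by itself. At the 37 blood patients in IV.B, power is 77.7%, slightly below the stated 80%, even if every one of them supplies a pair.

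**What to change.** In Appendix V, IV.C:

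1. Remove tissue, tumour-cell PD-L1 and infiltrating cells from the paired power statement. Alternatively, keep a tissue figure but calculate it for the number of baseline-progression pairs actually held. IV.C notes that results from this arm have already been presented, so these specimens can probably be counted.
2. State that any tissue pairs will be reported with estimates and confidence intervals only, without a power claim.
3. Reconcile the blood figure in IV.C and IV.D with IV.B. Either explain why 40 blood pairs are expected when 37 patients are listed, or restate the figure for 37 pairs: 77.7% power at 0.46 SD, or 80% power for about 0.47 SD.

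The cost is a few sentences in Appendix V and a less favourable stated power for tissue. No new samples are needed, and the primary analysis does not change.
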